8.5 A new treatment is added after the timepoint of 12 weeks

The patient can continue to participate in this study. The patient will cross over to the other treatment cohort and restart at time point 0. Further timepoints are at 4,12 and 24 weeks in this new treatment as mentioned earlier.

8.6 Treatment is stopped and another treatment is started

If the patient stops the treatment that is under investigation and starts a new therapy immediately, an end of treatment evaluation is performed. This end of treatment evaluation is then used as the first timepoint. Further timepoints are at 4, 12 and 24 weeks after starting the new treatment.

8.7 The patient proceeds to allogeneic stem cell transplantation

In case of proceeding to allogeneic stem cell transplantation this needs to be reported. An end of treatment evaluation is done before the start of conditioning therapy. After this, the study will stop for this patient. No further follow-up is needed.

8.8 The patient progresses to acute leukemia

In case the patient progresses to acute leukemia an end of treatment evaluation is performed after the patient is aware of the diagnosis. A follow-up is performed afterwards, as described below.

8.9 The patient develops another malignant disease

In case the patient develops a new malignancy (apart from non-invasive skin cancers) that requires treatment during the treatment currently under investigation, an end of treatment evaluation will be performed and the patient will drop out of this study.

8.10 The patient dies during the study period

In case the patient dies during the study, the cause of death needs to be reported to the coordinating center.

8.11 End of treatment

An end of treatment evaluation implies filling out the QUALMS and B-IPQ by the patient at time treatment is stopped before the timepoint at 24 weeks. This implies that data will be missing at one or more foreseen timepoints. At this moment, the end of treatment CRF form is completed by the treating physician. The patient will drop out of the study.

8.12 Follow-up

[figure not shown]
A follow up is needed after end of treatment, apart from patients that proceed to allogeneic stem cell transplantation or patients that are restart with immediately with another therapy. The QUALMS and B-IPQ are filled out by the patient at the follow-up time point, 4 weeks after end of treatment. The physician will fill out the follow-up CRF form. In case the patient starts a new treatment before the follow-up time point, the patient can be included again in this new treatment group at timepoint 0.

8.13 Sequential inclusion of the same patient

In case the patient meets inclusion and exclusion criteria at a later stage, participation is allowed after filling out the application form. The same unique patient code will always be used for the same patient,

even when he drops out of the study and is included again afterwards. When included again the patient will always start at timepoint 0.

Figure 1: Flowchart Treatment Scenarios

9 Treatments studied

As mentioned before, treatment options in regard to MDS are limited for the moment. In this study, we aim to evaluate 7 treatment groups. Patients included in an interventional trial with a treatment not included in one of the 7 groups can be included but will not be part of the statistical analyses. However, the data of those patients will be reported. Specific side effects of the different treatments need to be reported as mentioned in the study safety paragraph. The different treatment groups are:

9.1 Packed cells transfusions without other treatments.

This group contains patients receiving packed cell transfusions at a rate that is determined by the treating hematologist and at a hemoglobin threshold or with a hemoglobin goal determined by the treating hematologist. In this group only patients will be evaluated who did not receive any transfusions in the past in regard to their diagnosis of MDS. The first QUALMS can be filled out during the first transfusion. In case transfusion is urgent, the first QUALMS can be filled out until 2 weeks after the first transfusion. In this case the patient must be asked to fill out the questionnaires as he was before the first transfusion. Beyond two weeks of the first transfusion we do not consider the patient to be able to recall their situation precise enough to fill out the questionnaires in retrospect. When the questionnaires are filled out in retrospect, the date of first transfusion will be taken as time point 0. The next measuring point is 4 weeks after the first transfusion as mentioned earlier. Since transfusion instantly contributes to a better hemoglobin value, we expect to measure an immediate impact on QOL.

9.2 Erythropoietin stimulating agents

Erythropoietin stimulating agents (ESA) are used frequently in low risk MDS patients. Different pharmaceutical companies provide ESA in medical need programs. This study will not differentiate between darbepoietin alfa or epoietin alfa/beta. We will not interfere with medical need programs. Obtaining and administering this medication remains the full responsibility of the treating hematologist as this study is observational only.

9.3 Deferoxamine (Desferal®)

This is a frequently used iron chelator. Administration is possible via different routes apart from oral administration. No difference will be made depending on the route or dose that is used for administration of the medication.

9.4 Deferasirox (Exjade®)

Desferasirox is an oral iron chelator. The formula was changed recently with a positive impact on tolerance of this medication (9). This study will not differentiate between different doses of the medication that are used.

9.5 5'azacytidine (Vidaza®)

5'azacytidine is an old molecule that was first developed in the sixties. Renewed interest resulted from its role as a de novo methyl transferase (DNMT) inhibitor. Registered as Vidaza®, 5'azacytidine became one of the few options available for non-transplant eligible patients suffering from myelodysplastic syndromes. Administration is subcutaneous during 7 consecutive days every 28 days or in a 5+2 regimen with a pause during the weekend. Some physicians extend treatment cycles beyond the recommended 4 weeks (28 days). This adaptation is the responsibility of the treating hematologist and must not be reported. Median time to response is 4 to 6 cycles.

9.6 Lenalidomide (Revlimid®)

Revlimid is only reimbursed in patients suffering from low risk transfusion dependent MDS with a unique deletion in the long arm of chromosome 5 (del(5q)). Since this is a rare entity with an incidence of about 20 per year in Belgium, we hope to include as much patients as possible. This medication is also used as 'ad-on' in clinical studies. Patients starting with lenalidomide together with another MDS treatment are excluded from the study as stated in the exclusion criteria (Patients starting multiple treatments at the same moment are excluded).

9.7 Intensive chemotherapy

This therapy is frequently used to reduce disease burden in anticipation to allogeneic stem cell transplantation. Without stem cell transplantation, a durable remission can be obtained but will bring no cure. Different regimens can be used. Intensive chemotherapy is considered to be high dose chemotherapy that is administrated intravenously in the hospitalized patient resulting in a prolonged period of neutropenia. No difference will be made between different regimens that are used. Since this treatment comes with his own peculiar physical and psychological impact other treatments may be started at the same moment. If the patient is treated with intensive chemotherapy he will be evaluated in the intensive chemotherapy-group only from the moment he starts this treatment.

10 Study procedures

Patients will be asked to fill out the QUALMS and the B-IPQ before starting treatment or before the start of a new therapy. The first visit, patients fill out the QUALMS and B-IPQ will be between 2 weeks before starting this therapy and the actual moment of their new treatment.

Repeated testing using the QUALMS and B-IPQ will be done 4, 12 and 24 weeks after the actual start of therapy. The treating hematologist will be asked to fill out a case report form (CRF), every time the QUALMS and B-IPQ are filled out by the patient. All questionnaires must be filled out on site only. It is not allowed to take the questionnaires home. The first QUALMS and B-IPQ must be filled out in the ambulatory setting.

10.1.1 Quality of Life

QOL will be assessed by using of the QUALMS:

The QUALMS is a disease specific questionnaire for patients suffering from a myelodysplastic syndrome. This questionnaire was developed by Abel and colleagues at the Dana-Farber institute and has been validated in an international study (1). The Dana-Farber institute, who holds editorial rights, cannot be held responsible in any way for any damage, physical or psychological that resulted from the use of their questionnaire. The data collected by the use of this questionnaire will be intellectual property of the sponsor.

10.1.2 Illness perception

Illness perception will be assessed by means of the B-IPQ:

Illness perception is the idea a patient has about his or her disease and the meaning that is given to that particular idea. This perception can change during the course of a treatment. Since this perception may have an impact on the psychological well being of a patient, it is not unlikely that this will influence the patients' quality of life. To measure this perception, a validated questionnaire is used in his brief form, the B-IPQ (Brief illness perception questionnaire) (2).

11 Withdrawal of patients or premature termination of the study

11.1 Withdrawal of individual patients from protocol treatment

Patients should be withdrawn from protocol if any of the following criteria for withdrawal are met:

- ◆ Death
- ◆ Patient receiving different treatments within a timespan that is not allowed according to this protocol as mentioned earlier
- ◆ Patients developing another malignancy
- ◆ Patients progressing to acute leukemia
- ◆ Patients proceeding to allogeneic stem cell transplantation

Patients are allowed to withdraw from the study at any time for any reason if they wish to do so without any consequences. The investigator can also decide to withdraw a patient from protocol for other reasons than the criteria described above.

12 Safety

12.1 Reporting of adverse events.

An adverse event (AE) is any unfavourable and unintended sign (including an abnormal laboratory finding), symptom, or disease temporally associated with the use of a medical treatment or procedure that may or may not be considered related to the medical treatment or procedure. In contrast, an adverse reaction is characterized by the causal relationship between a medicinal product and any negative occurrence. The Belgian law recommends all physicians to report adverse reactions to the federal agency for medicines and health products (famhp) by use of the yellow paper or online.

Due to the purely non-interventional nature of this study, reporting to the sponsor should be done as per legislation for spontaneous reporting. In case an adverse reaction occurs, a parallel reporting to the famph and to the coordinating centre of this study must be performed. The coordinating centre (sponsor) will forward this report to Celgene. A general understanding to any occurred adverse events in the preceding period will come forward in the CRF that will be filled out during follow-up as outlined previously.

In case pregnancy occurs during study while the patient is taking an 'imid' drug, the drug must be stopped immediately and reporting should be done by the local investigator in accordance with the obligatory pregnancy prevention program (PPP) before prescribing an 'imid' drug.

12.2 Study Report

If the Regulations require that the Sponsor or the Principal Investigator submits a report to the competent authority or ethics committee about the Study upon completion or premature-termination of the study. The sponsor of the study shall provide a copy of that report to Celgene.

If the Regulations do not impose that obligation upon the Sponsor or the Principal Investigator, the Sponsor shall prepare a report regarding the Study. The Study report shall contain a presentation of the study objectives, the study design, the statistical methods and the outcome of the analysis of the data collected for the purpose of the Study. The Sponsor shall provide a copy of that report to Celgene.

13 Endpoints

13.1 Primary endpoint

Change in QUALMS score at timepoint 4 – 12 – 24 weeks after the start of a new treatment.

13.2 Secondary endpoints

- Change in B-IPS score at timepoint 4 – 12 – 24 weeks after the start of a new treatment
- Association between B-IPQ and QUALMS score.
- Association between clinical and disease specific factors and QUALMS score
- Association between transfusion threshold and QUALMS score.

- Association between hematological response and QUALMS score

14 Statistical considerations

14.1 Patient numbers and power considerations

The study will include 50 patients per treatment of interest. Assessing the change in QOL for seven different treatments hence results in a final sample size of 350.

14.2 Statistical analysis

At 5% significance level and 80% power, the proposed study needs to include 50 patients per group (with a group being a treatment of interest) in order to be able to detect a difference of 7.5 points in the QOL score. We hereby assume that the quality of life, as assessed by the QUALMS questionnaire, has a standard deviation of 15 points in all groups. This estimate was taken from the QUALMS validation study who assessed QOL using the QUALMS questionnaire in 255 MDS patients living in the US, Canada or Italy.

Treating the QOL as a normally distributed parameter, we computed sample size based on paired t-tests comparing the QOL at the follow-up time-points with the QOL at the start of the study, resulting in three pairwise comparisons of the following form:

$$H_0: \mu_i = \mu_j$$

$$H_A: \mu_i \neq \mu_j$$

with $i = (0, 0, 0)$ and $j = (4, 12, 24)$

Because multiple comparisons are made using the same data, the significance level for sample size calculations was adjusted using a Bonferroni correction to 0.016, which results in a sample size (per treatment group) of 45.20.

Accounting for the possibility of patients to drop out of the study, this sample size is increased with 10%, resulting in a sample size (per treatment group) of 49.72, and hence a need to include 50 patients for each treatment of interest.

During an interim analysis (after approximately 4 months), we will assess the sample size needed to detect a difference of 7.5 points, based on an estimate for the standard deviation in the specific study populations, and the sample size will be adjusted accordingly.

14.3 Statistical analysis

The differences in QOL will be studied by means of a linear mixed model with time as categorical covariate. By including a random intercept per patient, we account for the correlation arising from repeatedly measuring the same patients. Post-hoc comparisons will be made to compare the QOL after 4, 12 and 24 weeks with the baseline measurements.

Similarly a linear mixed effects model will be used to examine the differences in disease perception. The impact of disease perception on QOL will be assessed by a linear mixed model with QOL as outcome, disease perception as covariate and a random intercept per patient. In the same way, the relationship between QOL and clinical and disease specific factors will be studied.

More details on the statistical procedures can be found in the statistical analysis plan.

Analyses will be performed by a certified statistician, using statistical software programs R and SAS. A significance level of 0.05 will be maintained and all estimates will be accompanied by 95% confidence intervals.

15 Trial conduct and Registration

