4.3 QOL assessment in MDS

To assess the QOL in the general population, different tools were developed in the past. Mostly they consist of questionnaires that try to cover all relevant topics that might have an influence on the quality of life.

If a subgroup of the population is approached, different topics become more relevant. For example, living above a supermarket at the age of 75 can have a totally different impact on QOL than at a younger age and working night shifts.

Fatigue as a result of anemia is the most frequent symptom of myelodysplastic syndromes. Assessment of QOL in the MDS population focused on this in the past. The FACT (functional assessment of cancer therapy) questionnaires for anemia (FACT-AN) and fatigue (FACT-Fatigue) were used to evaluate the efficacy of ESA (7). Higher risk diseases have been approached with focus on the malign aspect of the disease, using the EORTC C30 (8). However, since those assessments do not necessarily cover the subtleties of the disease, a specific questionnaire was developed. The use of this questionnaire gives us a specific assessment for disease-related symptoms and psychological sequelae of MDS patients (1). This specific questionnaire, the QUALMS will be used in this study to evaluate the QOL of patients suffering from MDS.

5 Study objectives

With growing sense of self-determination in Belgium, QOL becomes more relevant than it used to be. With this study, we aim to:

Primary objective:

assess the impact of newly started treatments on the QOL of patients suffering from myelodysplastic syndromes.

Secondary objectives:

- assess the impact of newly started therapy on disease perception in MDS patients.
- study the relation between disease perception and quality of life
- examine which clinical and disease specific factors determine QOL in MDS patients
- collect information on the transfusion threshold in Belgian hematological centers and evaluate the impact on quality of life.
- evaluate whether changes in QOL are related to hematological responses.

This study will not mutually compare the effect that different treatments have on QoL since the studied treatments will be installed at different stages of the disease and have different indications.

6 Study design

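### Section 14.3 specifies no visit term and a single blended slope for the perception model, so a shared time trend can be reported as an impact of perception on QOL

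*Combined protocol and SAP*

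**What the plan says.** Section 14.3 gives the primary QOL analysis as a "linear mixed model with time as categorical covariate", with a random intercept per patient. For the secondary question it says: "The impact of disease perception on QOL will be assessed by a linear mixed model". The QOL score is the dependent variable, and the only other components listed are "disease perception as covariate and a random intercept per patient". No visit term, treatment term or split of the covariate is listed. The next sentence extends this form: "In the same way, the relationship between QOL and clinical and disease specific factors will be studied". The section then adds: "More details on the statistical procedures can be found in the statistical analysis plan". That plan is not part of the text reviewed.

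The objective in section 5 is to "study the relation between disease perception and quality of life", and section 13.2 names an association between the B-IPQ and QUALMS scores. Neither says whether the relation is between patients or within a patient over time. Sections 13.1 and 13.2 make change in each score an endpoint at the same visits (weeks 4, 12 and 24). The protocol does not say whether the association models are pooled over the seven treatment groups or fitted group by group.

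**The concern.** Both scores are measured repeatedly after the start of a treatment, and the protocol expects movement. Section 9.1 anticipates an immediate QOL effect of transfusion, and section 10.1.2 says perception can change during treatment. If both scores move after baseline for whatever reason, a model without a visit term credits the common movement to perception.

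A random intercept does not separate the two kinds of association either. With a covariate that varies over visits, the one slope is a weighted average of two quantities: how patients with worse perception differ in QOL from other patients, and how a patient's QOL moves when that patient's perception moves. Calling that average an impact invites the second reading. At stake is a published statement that perception affects QOL when the data may show only a common time course or stable differences between patients.

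**Working it through.** **The plan's own figure.** The documents give no figure for the association models. The sample size in section 14.2 does reproduce: a two-sided paired t-test with d = 7.5/15 = 0.5, alpha 0.016 and power 80% gives 45.20. Then 45.20 × 1.1 = 49.72, rounded to 50, and 7 × 50 = 350. It does not bear on this point except to supply n = 50 and n = 350.

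**Inputs from the documents.** QUALMS SD 15, a 7.5-point difference used as the shift, four visits (weeks 0, 4, 12, 24), n = 50 or 350.

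**Assumed inputs, because the documents give none.** B-IPQ SD 12; B-IPQ shift −3 or −6; share of variance lying between patients 0.5 or 0.7 on both scales; both shifts appear at week 4 and persist. The true within-patient link is zero.

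**Expected slope by formula, shift −6, share 0.5, no between-patient correlation.**
- Step pattern (0, 1, 1, 1): mean 0.75, sum of squares 0.75, divided by 3 = 0.25.
- Within-patient covariance from the trend: 7.5 × (−6) × 0.25 = −11.25.
- Within-patient variance of B-IPQ: 144 × 0.5 + 36 × 0.25 = 81. Within-patient slope without a visit term: −11.25/81 = −0.139.
- Within-patient variance of QUALMS: 225 × 0.5 + 56.25 × 0.25 = 126.56. Weight of the within part: 3 × 81/126.56 = 1.92.
- Variance of patient means: B-IPQ 72 + 72/4 = 90; QUALMS 112.5 + 112.5/4 = 140.6. Weight of the between part: 90/140.6 = 0.64, with slope 0.
- Blended slope: 1.92 × (−0.139)/(1.92 + 0.64) = −0.104.
- Standard error about 1/√(n × 2.56): 0.088 at n = 50 and 0.033 at n = 350, so z is about −1.2 and −3.1.

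**Simulation, shared trend only.** REML random-intercept fits, Wald test at two-sided 0.05; 800 runs at n = 50 and 400 at n = 350. Each pair is n = 50 / n = 350.

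| B-IPQ shift | Between share | Slope by formula | Mean simulated slope | Significant, as written | Visit term added | Visit term and split |
|---|---|---|---|---|---|---|
| −3 | 0.5 | −0.056 | −0.053 / −0.053 | 8.5% / 34.0% | 5.1% / 7.0% | 5.1% / 5.2% |
| −3 | 0.7 | −0.090 | −0.087 / −0.092 | 15.0% / 75.0% | 4.8% / 2.8% | 5.1% / 4.2% |
| −6 | 0.5 | −0.104 | −0.109 / −0.102 | 23.8% / 87.8% | 6.1% / 4.0% | 5.8% / 4.5% |
| −6 | 0.7 | −0.162 | −0.162 / −0.165 | 46.1% / 99.8% | 5.8% / 4.5% | 5.4% / 4.5% |

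The last column tests the within-patient slope; at n = 350 that model also has treatment group. Formula and simulation agree. With no trend and no correlation, the model as written rejects in 4.8% to 6.0% of runs, so the excess comes from the omitted visit term. Simulation error around 5% is √(0.05 × 0.95/400) = 1.1 percentage points at 400 runs.

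**Blending.** With no trend but a correlation of −0.3 to −0.5 between patients' stable levels on the two scales, the slope is significant in 13% to 38% of runs at n = 50 and 60% to 99.5% at n = 350. A visit term leaves this essentially unchanged. That is detection of a real between-patient association, not a false positive. It shows that the single slope responds to it while the within-patient link is zero. After the split, the within-patient slope rejects in 3.5% to 5.5%.

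**Treatment group.** With seven pooled groups, no trend, and group means spread over ±0.5 SD in opposite directions on the two scales, the model as written is significant in 32% of runs at n = 350. Adding visit and treatment group brings this to 6%.

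**The case against.** The strongest reply is that the objective asks about a relation and the endpoint about an association. A between-patient association answers both, so a reader who infers that the model fails the secondary objective goes too far. This stands. What remains is that the blended slope cannot say which association it reflects, and that section 14.3 labels it an impact.

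Three other stronger readings are tempting and not supported:
- *The rejection rates under between-patient correlation are false-positive rates.* They are not, because the simulated association is real and within the stated endpoint. Only the shared-trend rates are artefact.
- *The missing treatment term is an established error.* It matters if the seven groups are pooled, or if a patient contributes several treatment episodes under one code, as section 8.13 allows. Section 5 rules out comparing treatments, so group-by-group fitting is possible; the protocol does not say.
- *Every clinical-factor model has a blended slope.* A factor fixed at baseline has only a between-patient slope.

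It is also fair to say that section 14.3 defers detail to an analysis plan, which may add terms. The supportable statement is that the protocol specifies none. But the perception model's components are listed, and time is named for the primary model only, so the protocol sentence needs correcting or aligning in either case.

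Finally, if treatment improves perception and perception in turn improves QOL, a visit term removes the part of that relation that follows the common time course. This is a real cost, and the protocol does not say which quantity is wanted.

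**Conclusion.** The point holds for the perception model as section 14.3 describes it, and for clinical factors that vary over visits. With no within-patient link, a shared shift after baseline makes the slope significant in about 9% to 46% of runs at n = 50 and 34% to 99.8% at n = 350. The size rests on the assumed B-IPQ SD, B-IPQ shift and variance share, and on both scores moving at the same visits, which seven different treatments need not do alike. The mechanism does not depend on the exact values: if both scores shift on average, omitting visit biases the slope. These are secondary analyses. The primary model names time, and neither the primary endpoint nor the sample size is affected. The change should be made before analysis.

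**What to change.** In section 14.3, and in the analysis plan it refers to, replace the perception model with QUALMS on:
- visit (categorical);
- the patient's mean B-IPQ;
- the deviation of each visit's B-IPQ from that mean;
- a random intercept per patient;
- treatment group, if the seven groups are pooled or patients contribute more than one treatment episode.

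State whether the groups are pooled. Report the within-patient and between-patient slopes separately, and replace the word impact with association. Use the same structure for clinical factors that vary over visits. For factors fixed at baseline, add only the visit term and, if pooled, treatment group.

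The cost is a wording change and two slopes to report instead of one. Both questionnaires and the CRF are already completed at each visit (section 8.1), so no new data are needed. The report should note that the visit term removes any part of the relation that runs through the common time course.

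### The three QUALMS baseline contrasts are sized at a Bonferroni level of 0.016, but the analysis section names no adjustment and gives 0.05 with 95% intervals

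*Combined protocol and SAP*

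**What the plan says.** The primary endpoint (section 13.1) is the change in QUALMS score at weeks 4, 12 and 24 after a new treatment starts. Section 14.2 turns this into three two-sided paired comparisons with baseline. It begins from an overall level, "At 5% significance level and 80% power", and then lowers it: "Because multiple comparisons are made using the same data, the significance level for sample size calculations was adjusted using a Bonferroni correction to 0.016". That gives 45.20 patients per treatment group, and 49.72 after a 10% increase, hence 50. The variability assumption is that the score "has a standard deviation of 15 points in all groups".

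Section 14.3 describes the analysis: a linear mixed model with time as a categorical covariate and a random intercept per patient. Of the contrasts it says: "Post-hoc comparisons will be made to compare the QOL after 4, 12 and 24 weeks with the baseline measurements". It names no multiplicity method and no overall test that must come first. Its last sentence, which covers all analyses, is "A significance level of 0.05 will be maintained and all estimates will be accompanied by 95% confidence intervals". For further detail it points elsewhere: "More details on the statistical procedures can be found in the statistical analysis plan". No separate SAP is in the supplied text, and no other section of the protocol names an adjustment for the analysis.

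**The concern.** The contrasts that were sized are the contrasts that will be analysed. The reason section 14.2 gives for the correction, several comparisons on the same data, applies to the analysis just as much as to the sizing. Yet 14.2 ties the correction to the sample size calculation, and 14.3 gives 0.05 and 95% intervals without saying how they apply to a set of three.

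The decision rule for the primary endpoint is therefore open in the protocol. If each contrast is tested at 0.05, the study recruits extra patients for error control that it then does not use. If the rule is settled only after the data are seen, a change in the range where the two levels disagree could be called significant or not by choice.

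**Working it through.** **Inputs.** From section 14.2: two-sided test, 80% power, difference 7.5, SD 15, three contrasts per group, adjusted level 0.016, 10% increase. From section 14.3: 0.05, 95% intervals, random-intercept model. Assumed, because the documents do not give them: contrast correlations of 0.3, 0.5 and 0.7, and within-patient correlations r of 0.3, 0.5 and 0.7. With complete data, a random-intercept model makes the three contrasts correlate at 0.5 whatever r is, because they share the baseline.

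**Step 1: reproduce the sample size.** Paired t-test, noncentral t, standardised change 7.5/15 = 0.5, 80% power, solved for n:

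| Two-sided level | n | n × 1.1 |
|---|---|---|
| 0.016 | 45.20 | 49.72, so 50 |
| 0.05/3 = 0.0167 | 44.78 | 49.26, so 50 |
| 0.05 | 33.37 | 36.70, so 37 |

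The 0.016 row matches section 14.2 exactly, so the sizing did use the adjusted level. The correction costs 50 − 37 = 13 patients per group.

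**Step 2: false positives in a group with no true change.** P(at least one |Z| above the critical value) over three equally correlated contrasts, by numerical integration:

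| Contrast correlation | each at 0.05 | each at 0.016 |
|---|---|---|
| 0.3 | 13.6% | 4.6% |
| 0.5 | 12.5% | 4.3% |
| 0.7 | 10.9% | 3.8% |

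For reference, independence would give 1 − 0.95³ = 14.3% at 0.05.

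**Step 3: would an unstated overall time test be enough?** Simulation of the balanced random-intercept model (45 patients, 132 error degrees of freedom, 100,000 runs for each r):
- Nothing changes: contrasts at 0.05 after a significant overall F test at 0.05 give about 4% error.
- One time point truly changes by 7.5: the error on the two unchanged time points is about 9% with that gate, against 3.0% at 0.016. Once one time point has moved, the gate is nearly always open and no longer protects the others.

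**Step 4: which results depend on the reading?** SD of change = 15 × √(2(1 − r)), which is 17.75, 15.00 and 11.62 for r = 0.3, 0.5 and 0.7. The mixed-model standard error with 45 patients is √(2 × 225 × (1 − r)/45). At r = 0.5 this is 2.236. Critical values on 132 degrees of freedom are 1.978 (0.05) and 2.440 (0.016). Observed changes between 1.978 × 2.236 = 4.4 and 2.440 × 2.236 = 5.5 points are significant at 0.05 but not at 0.016. The band is 5.2 to 6.5 at r = 0.3 and 3.4 to 4.2 at r = 0.7.

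**Step 5: the price of adjusting.** Interval widths scale with the critical value: 2.440/1.978 = 1.23 for 0.016, and 2.376/1.978 = 1.20 for Dunnett. Paired-t power for a 7.5-point change:

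| SD of change | Evaluable n | at 0.05 | at 0.016 |
|---|---|---|---|
| 15 (r = 0.5) | 45 | 91% | 80% |
| 15 (r = 0.5) | 50 | 93% | 85% |
| 17.75 (r = 0.3) | 45 | 79% | 63% |
| 17.75 (r = 0.3) | 50 | 83% | 69% |

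**The case against.** A reader might infer that the two sections contradict each other, or that the primary analysis will be unadjusted. The documents support neither. Section 14.2 itself starts from 5% and applies Bonferroni inside it, so the 0.05 in 14.3 can be read as the same overall level. The sentence in 14.3 is a general closing statement that also covers B-IPQ and the association models; it was not written for these three contrasts alone. The 95% intervals could be meant as simultaneous. The cited SAP is a natural place for the contrast method and may already contain it.

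The practical stakes are also bounded. The study is observational, section 5 says treatments will not be compared with each other, and the disputed results at every correlation examined lie below the 7.5 points the study is sized to detect. The 12.5% figure belongs to one reading, with no adjustment and no gate. The correlation of 0.5 behind it needs complete data, while section 8.11 expects missing time points.

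These arguments limit the strength of the point but do not remove it. The family-wise reading is not stated anywhere in the protocol, and 95% intervals for every estimate most naturally read as unadjusted. A SAP that settles the matter should agree with a protocol that says the same. Over the correlations examined, the error under the literal reading stays above 10%.

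**Conclusion.** The point holds as an unstated rule and a mismatch between sections, not as proof of an uncontrolled analysis. Taken literally, section 14.3 gives about 12.5% family-wise error per treatment group (10.9% to 13.6% over the assumed correlations), where the level used for sizing gives about 4.3%. An overall time test alone would not close the gap. These figures assume the model is fitted within each treatment group; the 0.5 correlation also assumes complete data. The power figures depend on the SD of change. Section 14.2 describes 15 as the SD of the score but uses it as the SD of the change, and the two agree only if r = 0.5. Numbers per group may also move with the planned interim re-estimation. It should be fixed; confidence is medium because the SAP could not be seen.

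**What to change.** In section 14.3, and in the same terms in the SAP:
- State that 0.05 is the family-wise level for the three QUALMS baseline contrasts within each treatment group. State that there is no adjustment across the seven groups (7 × 3 = 21 contrasts), because treatments are not compared with each other.
- Test the three contrasts from the mixed model at 0.016 (or 0.05/3), or by a Dunnett-type method.
- Report matching intervals (98.4%, 98.33%, or simultaneous 95% for Dunnett), or keep 95% intervals and label them clearly as unadjusted.
- If an overall time test is meant to come first, say so, and keep the adjustment.

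This takes a few sentences and no extra patients, since 50 per group was already computed at 0.016. The cost is the wider adjusted intervals and the lower power per contrast shown in step 5. The loss is larger if within-patient correlation is below 0.5: at r = 0.3, power with 45 evaluable patients is about 63% rather than 79%.
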